#### 3.8.6 Vital Signs and Weight

Vital signs measurements include pulse rate, body temperature, systolic and diastolic blood pressure. Along with weight and BMI, they are assessed at screening and at following visits and may be unscheduled visits, if needed:

• Visit 1 (Screening Visit)

- Visit 2 (Placement Visit)
- Visit 3 (Week 6)
- Visit 4 (Week 13)
- Visit 5 (Week 26)
- Visit 6 (Week 52) or Early Discontinuation
- Long Term Follow up 1 (Year 2, Month 6)
- Long Term Follow up 2 (Year 2, Month 12)
- Long Term Follow up 3 (Year 3, Month 6)
- Long Term Follow up 4 (Year 3, Month 12)

Based on the visit window in the study protocol, new analysis visit windows are redefined as follows to cover every data point, including unscheduled visits.

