12.3.1 Monthly Phone Contact (up to 52 Weeks)

Subjects will be contacted by phone each month, after her menses, to confirm completion of the monthly diary for:

- The need for additional contraception;
- Use of concomitant contraception;
- Use of concomitant medications;
- Documentation of menstrual and intermenstrual bleeding;
- Assess if there have been any adverse events since the last contact; and
- Resolution of any prior serious adverse events or adverse events.

12.4 Long-term Follow-up post 52-week visit (Every 6 Months: Months 18-30 (±4wks) and 3 yrs (-3wks/+4wks) /Exit visit

The subject will return for follow up after their Week 52 visit, every 6 months, if they choose to continue with the study visit. During these visits, the subject will be evaluated for:

- Vital signs and weight
- General physical exam (same as at Screening Visit)
- Pelvic exam (string check)
- Transvaginal ultrasound to document VeraCept position (only if indicated)
- Pregnancy test, urine
- Interval and concurrent medications
- Adverse events
- Verify sexual activity

Document any back-up contraception methods

Additionally, at the final visit at 3 Years / Exit visit, the following will also be performed:

- Transvaginal ultrasound to document VeraCept position
- VeraCept Removal
- Urine pregnancy test will be done 17 days after removal/study exit by the subject at home, with a follow up call by the study coordinator or PI required to document results.

A 2-week supply of hormonal contraceptive pills will be provided to the subject by the site as a contraceptive option for the first two weeks after VeraCept removal.

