**Analysis Visit Windows for Safety and Other Outcome Measure Analyses** 

Visit	Target Day (of Study Day*)	Analysis Visit Window	Visit (Window) in Protocol
Visit 1/Screening		-1 or earlier	Visit 1/Screening
Visit 2	1	1	Visit 2 (Day 1)
Visit 3	42	2 – 67	Visit 3 (Week 6±2)
Visit 4	91	68 – 137	Visit 4 (Week 13±2)
Visit 5	182	138 – 273	Visit 5 (Week 26±2)
Visit 6	364	274 – 385	Visit 6 (Week 52±2)
Long Term FU 1	548	386 – 638	LTFU 1/Year 1 Month 6
Long Term FU 2	730	639 – 823	LTFU 2/Year 1 Month 12
Long Term FU 3	913	825 – 1003	LTFU 3/Year 2 Month 6
Long Term FU 4	1095	1004 +	LTFU 4/Year 2 Month 12

\* Study Day = Visit Date – VeraCept Placement Date + 1, for date on or after the study device placement; it = Visit Date – VeraCept Placement Date, for date before the study device placement.

Note that if there are 2 or more non-missing records in the same analysis visit window, only the last one (by the assessment date) will be used for summary table, but data listings will include all of them.

Body mass index (BMI) will be calculated numerically (= Weight in kilogram / square of Height in meter) and then categorized as: Underweight (< 18.5), Normal (18.5 – 24.9), Overweight (25.0 – 29.9), and Obese (≥30.0). Both numerical and categorical summaries for BMI will be presented. The 6-number summary statistics for continuous variables and their changes from baseline, as well as the number and percentage of subjects in each BMI category (Underweight, Normal, Overweight, and Obese), will be presented by analysis visit.

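### SAP 3.8.6 leaves Day 824 in no analysis visit window, and its unexplained Day 385 cut-off sends late Week 52 and 12-month exit visits to Long Term FU 1

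*SAP*

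**What the plan says.** SAP 3.8.6 lists the visits at which vital signs and weight are assessed, with one slot for "Visit 6 (Week 52) or Early Discontinuation". It then states that "new analysis visit windows are redefined as follows to cover every data point, including unscheduled visits". The table that follows, titled "Analysis Visit Windows for Safety and Other Outcome Measure Analyses", gives target days and windows by study day, with placement as Day 1:

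- Visit 5: target 182, Days 138 to 273
- Visit 6: target 364, Days 274 to 385
- Long Term FU 1: target 548, Days 386 to 638
- Long Term FU 2: target 730, Days 639 to 823
- Long Term FU 3: target 913, Days 825 to 1003
- Long Term FU 4: target 1095, Day 1004 onward

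Where one window holds several non-missing records, "only the last one (by the assessment date) will be used for summary table, but data listings will include all of them".

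The protocol allows 2 weeks either side of Week 52. The heading of Protocol 12.4 sets the later visits at "Every 6 Months: Months 18-30 (±4wks) and 3 yrs (-3wks/+4wks) /Exit visit". The SAP states no rule for choosing the boundaries and gives no reason for Day 385.

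**The concern.** There are two separate problems. First, the windows are meant to take in every record, yet one day belongs to none of them.

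Second, the Week 52 window is lopsided. It reaches 90 days before its target and 21 days after, and the remaining time goes to a Month 18 visit whose own protocol window opens months later. A Week 52 visit made a little late is labelled Month 18. If the woman continues and attends Month 18, the last-record rule removes the Week 52 visit from the summary. If she exits instead, she appears in an extension-phase column although she never entered the extension.

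The outputs at stake are Tables 14.3.9 (vital signs and weight), 14.3.10 (physical examination) and 14.3.11 (pelvic examination). All are planned for the Safety population, not the Extension population, so nothing filters out women who left at 12 months. SAP 3.8.8 also summarises device position by analysis visit. Between placement and the final exit visit, Week 52 is the only scheduled visit at which Protocol Table 1 marks ultrasound for every woman, so the displaced record may be her one routine ultrasound check of position in that period.

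**Working it through.** **Inputs.** Target days and window limits come from the SAP 3.8.6 table. Protocol windows come from Protocol Table 1 and sections 12.3 and 12.4.

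**Step 1: coverage.** Listing every study day from 1 to 1200 against the stated windows leaves one day unassigned, Day 824 (823 + 1 = 824, and the next window starts at 825). Around the SAP targets, the protocol window for Month 24 is 730 ± 28 = Days 702 to 758, and for Month 30 it is 913 ± 28 = Days 885 to 941. Day 824 lies outside both, so only an unscheduled, removal or badly mistimed visit would fall on it.

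**Step 2: boundaries against target midpoints,** (t1 + t2)/2.

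| Boundary | Targets | Midpoint | Stated end / next start | End minus midpoint |
|---|---|---|---|---|
| Visit 3 / Visit 4 | 42, 91 | 66.5 | 67 / 68 | +0.5 |
| Visit 4 / Visit 5 | 91, 182 | 136.5 | 137 / 138 | +0.5 |
| Visit 5 / Visit 6 | 182, 364 | 273 | 273 / 274 | 0 |
| Visit 6 / Long Term FU 1 | 364, 548 | 456 | 385 / 386 | −71 |
| Long Term FU 1 / FU 2 | 548, 730 | 639 | 638 / 639 | −1 |
| Long Term FU 2 / FU 3 | 730, 913 | 821.5 | 823 / 825 | +1.5 |
| Long Term FU 3 / FU 4 | 913, 1095 | 1004 | 1003 / 1004 | −1 |

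Six of the seven window ends lie within 1.5 days of the midpoint. The Visit 6 end is 71 days before it.

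**Step 3: what Day 385 corresponds to.** 364 + 21 = 385. The protocol window for Week 52 is 364 ± 14 = Days 350 to 378, so the cut-off contains all of it plus 385 − 378 = 7 days. The protocol window for Month 18 opens at 548 − 28 = Day 520.

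**Step 4: days nearer Week 52 but labelled Long Term FU 1.**
- Day 386 is 386 − 364 = 22 days from Week 52 and 548 − 386 = 162 days from Month 18.
- Day 455 is 91 and 93 days away respectively, so it is still nearer Week 52.
- Day 456 is 92 days from both, a tie.
- The strictly nearer days are 386 to 455: 455 − 386 + 1 = 70 days.

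**Step 5: tracing a Week 52 visit made on Day 390.**
- *The woman continues and attends Month 18 on time (Days 520 to 576).* Both records fall in Days 386 to 638, and "only the last one (by the assessment date) will be used for summary table". The Day 390 record leaves the summary, and Visit 6 has no value unless some other record falls in Days 274 to 385.
- *The woman exits at that visit.* Her record stays in the summary, but under Long Term FU 1.

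**The case against.** The strongest reply is that the midpoint rule is read into the table. The SAP never states it, and 3.8.6 says the windows are derived from those in the protocol. Day 385 holds the full protocol window and a further week, and it is the only boundary where the 12-month study meets the extension, which the SAP treats as a separate phase with its own population. That may be a deliberate split. This stands. A reader might infer that Days 386 to 456 are assigned to the wrong visit, but the documents support only that the boundary departs from the pattern of the others without explanation, and that the labelling in Step 5 follows from it.

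A reader might also conclude that the obvious repair is to run Visit 6 to Day 456. That would bring its own displacement. A woman seen on time at Day 364 who has an unscheduled extension visit on Day 430 would have her scheduled Week 52 record replaced under the last-record rule. The present cut-off prevents this. Extension removals on Days 386 to 456 would also move into the Week 52 column. Further, SAP 3.1.2 says the 1-year analysis has been done and was the main analysis, so Week 52 summaries could come to differ from outputs already produced.

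A reader might put a count on the harm: if 2% to 10% of about 200 Week 52 visits fell after Day 385, 4 to 20 women would be affected. Neither input is in the documents, and the true number could be zero.

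Finally, the affected summaries are descriptive. The Pearl Index is computed from dates (SAP 3.7), the adverse event tables use their own day ranges (3.8.2), and removal and expulsion rates are handled separately (3.8.3 and 3.8.4). This also stands. None of these replies touches the Day 824 gap, which contradicts the SAP's own statement.

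**Conclusion.** The point holds, at minor severity. The Day 824 gap is a plain error of one day, and few if any records are likely to fall on it. The Day 385 cut-off is not shown to be an error, but it is unexplained and has a real effect: a scheduled Week 52 or 12-month exit visit from Day 386 on is summarised as Long Term FU 1, and it leaves the summary if another non-missing record follows by Day 638. Visits up to Day 385 are unaffected. An extension removal near Month 18, say on Day 550, is correctly placed and is not part of this point.

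The conclusion rests on applying the table and the last-record rule as written, with no mapping by nominal visit, since the SAP describes none. The documents do not show how many visits took place after Day 385, so the number of misplaced or displaced records cannot be given. No efficacy result or adverse event table changes.

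**What to change.** 1. **Close the gap.** Start Long Term FU 3 at Day 824. Alternatively use Days 639 to 821 for Long Term FU 2 and 822 to 1003 for Long Term FU 3, which also follows the target midpoint (821.5).
2. **Keep Day 385 for unscheduled records, and state the reason for it.** Assign scheduled Week 52 and 12-month exit visits held after Day 385 to Visit 6 by their nominal CRF visit. Confine this to those visits: Protocol Table 1 has earlier removals complete the Visit 6 activities too, and they should stay with the day windows, as should extension removals.
3. **Within a window, give scheduled visits priority over unscheduled ones,** with the last-record rule applied after that.
4. **Document any Week 52 value that then differs from the completed 1-year outputs.** The priority rule acts on every window, so the same applies to any earlier Year 1 value it changes.

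The cost is an edit to one SAP table and its note, plus a small programming change. No new data are needed. The downside is that a few Week 52 summary values may change, and some will be dated more than 21 days after target.

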**Analysis Visit Windows for Safety and Other Outcome Measure Analyses** 

Visit	Target Day (of Study Day*)	Analysis Visit Window	Visit (Window) in Protocol
Visit 1/Screening		-1 or earlier	Visit 1/Screening
Visit 2	1	1	Visit 2 (Day 1)
Visit 3	42	2 – 67	Visit 3 (Week 6±2)
Visit 4	91	68 – 137	Visit 4 (Week 13±2)
Visit 5	182	138 – 273	Visit 5 (Week 26±2)
Visit 6	364	274 – 385	Visit 6 (Week 52±2)
Long Term FU 1	548	386 – 638	LTFU 1/Year 1 Month 6
Long Term FU 2	730	639 – 823	LTFU 2/Year 1 Month 12
Long Term FU 3	913	825 – 1003	LTFU 3/Year 2 Month 6
Long Term FU 4	1095	1004 +	LTFU 4/Year 2 Month 12

\* Study Day = Visit Date – VeraCept Placement Date + 1, for date on or after the study device placement; it = Visit Date – VeraCept Placement Date, for date before the study device placement.

Note that if there are 2 or more non-missing records in the same analysis visit window, only the last one (by the assessment date) will be used for summary table, but data listings will include all of them.

Body mass index (BMI) will be calculated numerically (= Weight in kilogram / square of Height in meter) and then categorized as: Underweight (< 18.5), Normal (18.5 – 24.9), Overweight (25.0 – 29.9), and Obese (≥30.0). Both numerical and categorical summaries for BMI will be presented. The 6-number summary statistics for continuous variables and their changes from baseline, as well as the number and percentage of subjects in each BMI category (Underweight, Normal, Overweight, and Obese), will be presented by analysis visit.

#### 3.8.7 Physical Examination

Physical examination will be performed at the same visits as vital signs in the following body areas:

- General Appearance
- Skin
- HEENT
- Thyroid
- Lung
- Back
- Heart
- Abdomen
- Extremities
- Neurological

The examination results ("Normal" or "Abnormal"), and changes from baseline ("Improved" – if "Abnormal" at baseline and "Normal" at post-baseline, "No Change", "Worsened" – if "Normal" at baseline and "Abnormal" at post-baseline), will be summarized by presenting the number and percentage of subjects in each category by body area at each analysis visit.

#### 3.8.8 Pelvic Examination

Pelvic examination will be performed at the same visits as vital signs to verify the VeraCept position with the following 3 questions on the CRF (in addition to those in the "Gynecological Examination" section 3.5.4, which were assessed at baseline visit only).

- Was a Transvaginal Ultrasound Performed? (Yes, No)
- Was a Manual String Check performed? (Yes, No)
- Is the device in the proper position? (Yes, No)

The device in the proper position will be summarized categorically by analysis visit. The pelvic exam methods will also be summarized by presenting the number and percentage of subjects who had

- only ultrasound performed
- only manual string check performed
- both ultrasound and manual string check performed.

## 3.8.9 Monthly Phone Contact

Monthly phone contact will be carried out for 1 year (12 months) since the study device placement. The data summary (where months are defined as 30-day intervals from VeraCept placement date) will include the following 3 questions by presenting the number and percentage of subjects in each category for the first 2 questions, and 6-number statistics for the last one.

- Was there a need for additional contraception? (Yes, No)
- Did you have intercourse at least one time in the last month? (Yes, No)
- Approximately how many times since the last phone call have you had intercourse?

## 3.8.10 Long Term Follow Up Visits

Long term follow-up office visits for additional 2 years will occur every 6 months for those subjects who continue study device use after 1 year (52 weeks). In addition to vital signs, physical exam, pelvic exam, etc., as those shown in Section 5.1 "Study Schedule of Assessments", the assessments also include the following 3 questions which will be summarized categorically with number and percentage of subjects provided for each answer.

- Did you have vaginal intercourse at least once since your last visit? (Yes, No)
- Did you use any additional birth control methods in the past 6 months? (Yes, No)
- How often has the subject had vaginal intercourse in the past 6 months? (Not Once, Once a month or less, Several Times a Month, Once or Twice a week, Several Times a week, At least once a day)

## 3.8.11 Cycle Contact

In addition to being used in the efficacy analysis for EP population, cycle contact data will be summarized by the number and percentage of "Yes" and "No" answers to each question by contact cycle for Extension population subjects.

#### 3.8.12 Return to Fertility

Any subject who discontinues for desire to get pregnant will have a follow-up call to be completed 6 months after discontinuing. In addition to data listing, the following summaries will also be presented, with the percentages (%) based on the total number of subjects who discontinue due to desire to get pregnant:

- Number (%) of subjects got pregnant
- Number (%) of subjects got pregnant in 1, 2, 3, 4, 5 and 6 months
- Number (%) of subjects did not get pregnant
- Number (%) of subjects with 1, 2, 3, 4, 5 and 6 months of follow-up for those not pregnant.

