Investigational

Site Information: This study will be conducted at up to 14 centers in the U.S

Follow-up: Physical assessment (office visit) will occur at weeks 6, 13, 26

and 52 after placement, with monthly telephone contact. For those subjects who wish to continue study device use after 12 months, follow-up office visits will occur every 6 months with contact at the end of each 28-day cycle beginning after the 52-week visit. Additional visits will be conducted if necessary for

safety issues.

Follow-up after early study device removal:

Subjects requesting VeraCept removal to become pregnant will be followed to pregnancy or until the subject changes her mind about trying to get pregnant. All subjects in whom VeraCept is removed prior to 12 months, for any reason, will be required to use an alternative contraceptive for the first two weeks following removal. Hormonal contraceptive pills will be reimbursed by the sponsor as a contraceptive option during this time unless the subject has a category 4 condition precluding their use.

Study Population:

Pre-menopausal women ages 18 – 40, at risk for pregnancy, who are interested in using an intrauterine contraceptive for birth control will be eligible for this study. Subjects must provide written informed consent and meet the study subject selection criteria without any exclusions as outlined in the Clinical Investigation Plan (CIP).

Primary Effectiveness

Outcome:

The primary outcome measure is effectiveness, evaluated as the absence of pregnancy by 12 months, failure will be calculated by the Pearl Index.

Safety and Other Outcome

Measures:

Safety and other outcome measures include:

Study Device Placement:

- Ease of placement
- Placement success

Safety:

- Serious Adverse Events
- Adverse Events

Tolerability:

- Bleeding and spotting patterns
- Discontinuation rate and reasons for discontinuation

Subject Selection Criteria

INCLUSION CRITERIA

Subject must meet all of the following criteria to participate in this study:

- 1. Between 18-40 years of age at the time of study initiation;
 - 1.1 Enrollment will be targeted for 225 subjects aged 18-35 (for safety and effectiveness analyses) and an additional 25 subjects aged 36-40 (for safety only) (note: all subjects will be included in the analysis for device placement and tolerability);
- 2. Pre-menopausal, as determined by regular menstrual cycle (28 ± 5 days) for the last 3 months;

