12.5 Early Discontinuation Visit

Subjects who request removal of VeraCept before 12 months will be required to use an alternative contraceptive for the first two weeks following removal. A two-week supply of Hormonal contraceptive pills will be provided by the site as a contraceptive option during this time.

If a subject requests VeraCept removal because of an adverse event, the Study Exit Visit described in Section 12.3 above should be completed and documented on the CRF at the time of VeraCept removal. The subject will be followed until resolution of the event or 30 days after removal, whichever occurs first. Subjects experiencing an on-going adverse event will continue to receive the appropriate follow-up medical care.

If a subject requests early discontinuation and VeraCept removal to become pregnant, the Study Exit Visit described in Section 12.3 above should be completed and documented on the CRF at the time of VeraCept removal. Additionally, subjects shall be followed for either; six (6) months, until they decide to no longer try to conceive or they become pregnant, whichever comes first. Outcome data regarding subject's ability to conceive, or the decision to no longer try to become pregnant will be collected via phone contact and documented on the phone contact form.

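### The return-to-fertility percentages divide by every woman who discontinued to conceive and make no allowance for women who stop trying or are lost before six months

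*SAP*

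**What the plan says.** SAP 3.8.12 plans one descriptive table (14.3.15) and a listing. Each woman who leaves in order to conceive "will have a follow-up call to be completed 6 months after discontinuing". All percentages share one base: "percentages (%) based on the total number of subjects who discontinue due to desire to get pregnant". The rows are pregnancies overall and by month 1 to 6, then "Number (%) of subjects did not get pregnant", then "Number (%) of subjects with 1, 2, 3, 4, 5 and 6 months of follow-up for those not pregnant". There is no row, exclusion or censoring rule for a woman who stops trying or cannot be reached. The general conventions in SAP 3.1.3 would allow a denominator of non-missing observations, but they also let a specific section override them, so the full total applies here.

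Protocol 12.5 follows these women for "six (6) months, until they decide to no longer try to conceive or they become pregnant, whichever comes first", and says that "the decision to no longer try to become pregnant will be collected via phone contact". The protocol's Investigational Plan Summary describes the same follow-up as lasting until pregnancy or a change of mind, and gives no six-month limit.

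Both protocol places also say that women whose device is removed before 12 months "will be required to use an alternative contraceptive for the first two weeks following removal". For removal at the Week 52 and 3-year exit visits (Protocol 12.3 and 12.4), pills are described only as an option.

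**The concern.** A woman who stops trying after one month has been at risk of conceiving for one month. In the SAP's percentage she nevertheless weighs as much as a woman who tried for six months without success. The percentage therefore mixes three things: how readily women conceive after removal, how often they change their minds, and how often sites lose contact with them. The last two say nothing about fertility after the device, and both push the figure down.

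What is at stake is how one table is read. A low figure could be taken as slow return of fertility when part of it is short follow-up. The SAP also does not say from which day months 1 to 6 are counted. That affects the month-1 row most, because some women must use contraception for the first two weeks after removal.

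**Working it through.** **No plan figure to reproduce.** The documents give no number of women leaving to conceive, no conception rate and no target. The size can only be shown over assumed ranges.

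**Inputs**
- Denominator: all women who discontinued to conceive (SAP 3.8.12).
- Horizon: six months (SAP 3.8.12, Protocol 12.5).
- Monthly conception probability f among women still trying: assumed 0.10 to 0.25.
- Monthly share s of women not yet pregnant who stop or are lost, applied at the end of each month: assumed 0 to 0.10.

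**Formulas**
- Kaplan-Meier figure, censoring at stopping or loss: 1 − (1 − f)^6.
- SAP crude figure: the share still followed at the start of month m is r^(m−1), with r = (1 − f)(1 − s). The crude percentage is therefore f × (1 − r^6) / (1 − r).

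**One case in full**, f = 0.20 and s = 0.05:
- r = 0.80 × 0.95 = 0.76, and 0.76^6 = 0.193.
- Crude = 0.20 × (1 − 0.193) / 0.24 = 67.3%.
- Kaplan-Meier = 1 − 0.80^6 = 73.8%.
- The crude figure is 6.5 points lower.

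**Whole range** (six-month percentages; gaps from unrounded values)

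| f | Kaplan-Meier | crude, s = 0 | s = 0.02 | s = 0.05 | s = 0.10 | largest gap |
|---|---|---|---|---|---|---|
| 0.10 | 46.9 | 46.9 | 44.8 | 42.0 | 37.8 | 9.1 |
| 0.15 | 62.3 | 62.3 | 59.8 | 56.3 | 51.0 | 11.2 |
| 0.20 | 73.8 | 73.8 | 71.1 | 67.3 | 61.5 | 12.3 |
| 0.25 | 82.2 | 82.2 | 79.5 | 75.6 | 69.6 | 12.6 |

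The gap is zero when nobody stops or is lost, and about 13 points at the far corner.

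**The two weeks, taken separately.** If months are counted from removal and a woman does use contraception for 14 days, those days are 14/30 = 47% of a 30-day first month. With f = 0.20 and s = 0, the month-1 figure becomes 0.20 × (16/30) = 10.7% instead of 20.0%. The six-month figure becomes 1 − (1 − 0.107) × 0.80^5 = 70.7% instead of 73.8%. Across the grid the six-month effect on the crude figure is about 3 to 5 points. It applies only to women who used the contraception.

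**The case against.** The strongest reply is that SAP 3.8.12 already supplies almost everything needed. Pregnancies by month are the events, and months of follow-up among women not pregnant are the censoring times, so a reader can build the life table. Take 12 women. One conceives in each of months 1 to 6, four leave after 1, 2, 2 and 3 months, and two reach six months not pregnant. The planned rows would show exactly this. The risk sets are 12, 10, 7, 5, 4 and 3, so survival is 11/12 × 9/10 × 6/7 × 4/5 × 3/4 × 2/3 = 0.283. That is 72% conceiving, against a crude 6/12 = 50%. This reply largely stands: what is missing is the estimate more than the information. Two gaps remain. The percentage itself stays uncorrected, and a woman never reached has no place in rows that begin at one month.

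Several stronger readings are tempting, but the documents do not support them.
- *Fertility is understated.* This holds only if some women stop or are lost, and the documents do not say that any will.
- *Stopped or lost women are defined as failures.* This is an inference from the lack of any other outcome row. The follow-up row supports it for women with short follow-up. For lost women the SAP is silent.
- *The clock starts during required contraception.* The SAP does not define time zero; it only times the call. The two weeks are required only for removals before 12 months. Women enter intending to avoid pregnancy for 12 months, and nothing shows that many such removals would be made in order to conceive.
- *The error is 22 points.* That is the 12-woman example, in which a third leave within three months. It is an extreme case and not an estimate.
- *The table exists to prove reversibility.* No such purpose is stated. Return to fertility is in neither the objectives nor the endpoints of SAP 2.4.

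Kaplan-Meier has its own weakness. It assumes that stopping or loss is unrelated to fecundability. If women stop because they are not conceiving, it overstates conception.

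**Conclusion.** The point holds in a limited form. The specified percentage is a valid proportion of all women who left to conceive. As an estimate of six-month conception among women still trying, it is too low whenever anyone stops or is lost. The size is unknown: 0 to about 13 points under the assumed ranges, with stopping and loss taken as unrelated to fecundability. Where it occurs, the error makes return of fertility look slower than it is. The undefined time zero is a separate, smaller gap. The conflict between the Investigational Plan Summary and Protocol 12.5 over the length of follow-up is plain from the text. Because the table is descriptive and bears on no listed endpoint, this is a cheap improvement and not a flaw in the trial's main conclusions.

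**What to change.** In SAP 3.8.12 and Table 14.3.15:
- Keep the planned counts and crude percentages.
- Add separate rows for women who stopped trying and women lost to follow-up, and say how a woman with no contact at all is shown.
- Add a Kaplan-Meier or monthly life-table cumulative probability of conception through six months, with a 95% CI. Censor at the decision to stop trying, last contact or six months, whichever is first.
- State time zero, for example device removal. Add a note that removals before 12 months include two weeks of required contraception.
- State the assumption about stopping and loss, and show the crude figure beside the estimate for that reason.

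Separately, reconcile the Investigational Plan Summary with Protocol 12.5 on how long these women are followed.

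The cost is SAP wording and a few added rows in one table. Protocol 12.5 already collects the decision to stop trying. It does not say that the date is recorded, so the phone contact form should be checked. Follow-up in whole months, which the planned row needs anyway, is enough for a life table. The drawback is precision. In the 12-woman example, Greenwood's sum is 1/132 + 1/90 + 1/42 + 1/20 + 1/12 + 1/6 = 0.342, and the log-log 95% CI around 72% runs from about 40% to 96%.
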